### **5.2.2 IVRS/IWRS**

IVRS/IWRS will be used for allocation of enrolment number, management of study medication, open label extension enrolment (where applicable), emergency unblinding; specific IVRS/IWRS functionality will be in the IVRS/IWRS user manual.

The IVRS/IWRS technology will be managed and maintained by Perceptive. The system is accessible by telephone (IVRS) and computer (IWRS) 24 hours a day, 7 days a week. The IVRS/IWRS user manual will be provided to each centre.

### **5.3 Procedures for handling patients incorrectly randomised**

Patients who fail to meet the inclusion/exclusion criteria should not, under any circumstances, be randomised. There can be no exceptions to this rule.

Where patients that do not meet the selection criteria are randomised in error or incorrectly started on treatment or where patients subsequently fail to meet the study criteria post initiation or for patients that develop exclusion criteria, the investigator should inform the AstraZeneca Study Delivery Team Physician immediately. A discussion should occur between the AstraZeneca Study Delivery Team Physician and the Investigator regarding whether to continue or discontinue the patient from treatment, unless the investigator decides to stop study drug as it would put the patient at undue risk.

The AstraZeneca Study Delivery Team Physician is to ensure all such contacts are appropriately documented. In situations where an agreement cannot be reached, the patient should have their study therapy stopped.

Randomised patients remain in the trial for follow up visits regardless of whether or not the patient continues study medication unless patient documents his/her refusal to sign full informed consent form before first dose of active ticagrelor.

### **5.4 Blinding and procedures for unblinding the study**

#### **5.4.1 Methods for ensuring blinding**

Blinding of active and placebo tablets will be maintained by both the active and placebo tablets matching in size, shape, and placebo tablet matching in size, shape and appearance, and all outer packaging of each treatment arm will be identical.

#### **5.4.2 Methods for unblinding the study**

Individual treatment codes, indicating the treatment randomisation for each enrolled patient, will be available to the investigator(s) or pharmacists from the IVRS/IWRS. Routines for this will be described in the IVRS/IWRS user manual that will be provided to each centre.

The treatment code should not be broken except in medical emergencies when the appropriate management of the patient requires knowledge of the treatment randomisation. The investigator documents and reports the action to AstraZeneca without revealing the treatment given to patient to the AstraZeneca staff.

AstraZeneca retains the right to break the code for SAEs that are unexpected and are suspected to be causally related to an investigational product and that potentially require expedited reporting to regulatory authorities. Treatment codes will not be broken for the planned analyses of data until all decisions on the evaluability of the data from each individual patient have been made and documented.

## **5.5 Treatments**

### **5.5.1 Identity of investigational product(s)**

Investigational product	Dosage form and strength	Manufacturer
Ticagrelor	tablet, 90 mg	AstraZeneca or designated CRO
Ticagrelor placebo	tablet, placebo to match 90 mg	AstraZeneca or designated CRO

### **5.5.2 Doses and treatment regimens**

At Visit 1 (randomisation), eligible patients will be randomly assigned to one of two treatment groups:

- 2 tablets of ticagrelor (loading dose) taken in the ambulance followed by 2 tablets of matching placebo in the hospital, taken orally.

Or

- 2 tablets of matching placebo taken in the ambulance followed by 2 tablets of ticagrelor (loading dose) in the hospital, taken orally.

After that initial double blind period, all patients will continue on active ticagrelor 90 mg BID and will be followed in study for 30 days post randomisation.

Randomization will be managed by the ambulance personnel by opening the patient pack and administering the first dose of study medication. The second dose will be taken at Visit 2 before undergoing ECG and angiography

Subsequent maintenance doses should be taken morning and evening, at approximately 12-hourly intervals, for the remainder of the treatment period.

Study medication can be taken with or without food. Study medication should not be altered (eg, crushed, put in another vehicle) and should not be given by nasogastric tube or other routes.

The treatment for the entire study will be packaged so that it will follow the patient from the ambulance to the hospital. Individual patient treatment is defined as the double blinded loading dose (2x2 tablets), a bottle of ticagrelor 90 mg containing 64 tablets (30 days of active treatment + 2 days overage), and the Informed Consent Forms will be provided to each ambulance. Each treatment will be clearly identified.

### **Duration of treatment**

Patients will be randomised to treatment no later than 6 hours after the onset of cardiac ischemic symptoms. Approximately 12 hours after the second loading dose, the patient will continue on ticagrelor 90 mg BID as maintenance treatment and will be followed in study for 30 days post randomisation.

### **Interruptions to study medication**

No dose of ticagrelor or placebo blinded study medication should be missed.

In the event of this happening, this would constitute a major deviation to the study.

- If missed 1st loading dose in pre-hospital settings: for patient benefit, it is recommended that all 4 tablets are administered to the patient in hospital.
- If missed 2nd loading dose in the Cath Lab (i.e. loss of the patient bottle ): it is up to the investigator to decide the appropriate therapy for the patient during angiography.

Missed dose of ticagrelor active treatment during 30 days post randomisation should not be made up (ie, if a dose is missed the next regularly scheduled dose should be taken and should not be doubled).

A temporary interruption of ticagrelor active treatment is defined as a minimum of 4 missed doses of study medication and should be recorded in the eCRF.

#### **5.5.3 Labelling**

Labels will be prepared in accordance with Good Manufacturing Practice (GMP) and local regulatory guidelines. The labels will fulfil GMP Annex 13 requirements for labelling, including the study code and directions for use. Label text will be translated into local language according to local requirements.

#### **5.5.4 Storage**

All study medications should be kept in a secure place under appropriate storage conditions. The study medication label on the study supplies specifies the appropriate storage.

### **5.6 Concomitant treatment(s)**

#### **5.6.1 Oral antiplatelet therapies**

**Concomitant ASA** (Acetylsalicylic Acid (Aspirin)) : In addition to study medication, patients may receive 150–300 mg per os or 250 (–500) mg bolus i.v., in the double blind phase, followed by 75–100 mg daily as recommended by ESC/EACTS guidelines 2010 or up to 150 mg according to ticagrelor Summary of Product Characteristics.

The patient will be responsible for the ASA supply throughout the study. The ASA dose should remain constant throughout the study.

ASA for pain relief should, when possible, be discouraged and paracetamol (acetaminophen) given.

**Other oral anti-platelets: clopidogrel, prasugrel, ticlopidine, dipyridamole, and cilostazol:**

Concomitant treatment with any of these drugs is not allowed in the study.

**5.6.2 Non Steroidal Anti-Inflammatory Drugs (NSAIDs)**

Concomitant treatment with any of these drugs is not allowed in the study.

**5.6.3 GPIIb/IIIa receptor antagonists**

Upstream (in ambulance) use of GPIIb/IIIa receptor antagonists is not recommended as a concomitant treatment but will be left to physician's discretion. In lab use of GPIIb/IIIa receptors antagonists after the angiogram is possible and not discouraged. This use will have to be identified as being a strategy of choice or a bail out use during PCI.

Bail-out use of GPIIb/IIIa receptors antagonists is allowed for thrombotic complications (see section 6.3.2.5)

**5.6.4 Parenteral anticoagulants**

Short-term treatment with approved parenteral anticoagulants (eg. unfractionated heparin (UFH), low-molecular-weight heparin (LMWH), bivalirudin, fondaparinux) is allowed. However, long-term treatment with LMWH in outpatients (at venous thrombosis treatment doses) in combination with study medication is not allowed. Concomitant treatment with venous thrombosis prophylaxis doses is allowed.

**5.6.5 Oral anticoagulants**

Concomitant treatment with oral anticoagulant drugs is not permitted during the study.

**5.6.6 Fibrinolytics**

A patient is not eligible for inclusion into the study if fibrinolytic therapy has been given in the 24 hours prior to randomisation or is planned to be administered for STEMI or any other condition.

Fibrinolytic treatment is not permitted during the study.

### **5.6.7 P-glycoprotein interactions**

No data are available on concomitant use of ticagrelor with potent P-glycoprotein (P-gp) inhibitors (e.g. verapamil, quinidine, cyclosporin) that may increase ticagrelor exposure. If the association cannot be avoided, their concomitant use should be made with caution. Ticagrelor modestly increases digoxin levels. Therefore digoxin levels should be monitored closely following initiation of study medication and with any change in study medication. Other p-glycoprotein substrates may be expected to have similar changes in pharmacokinetics. For additional details reference the Summary of Product Characteristics.

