## **4.2 Exclusion criteria**

Patients should not enter the study (or for exclusion criterion n° 2, not continue in study) if any of the following exclusion criteria are fulfilled:

1. Expected time to 1st PCI balloon inflation in the hospital, from the qualifying ECG is more than 120 minutes.
2. Patient's refusal to sign full version of the Informed Consent Form before first intake of active ticagrelor 90 mg BID
3. Concomitant oral or intravenous therapy with strong cytochrome P450 3A (CYP3A) inhibitors which cannot be stopped for the course of the study.
  - Strong inhibitors: ketoconazole, itraconazole, voriconazole, telithromycin, clarithromycin (but not erythromycin or azithromycin), nefazadone, ritonavir, saquinavir, nelfinavir, indinavir, atazanavir, over 1 litre daily of grapefruit juice.
4. Contraindication to ticagrelor (e.g. hypersensitivity to the active substance or to any of the excipients, active pathological bleeding, history of previous intracranial bleed, moderate to severe hepatic impairment).
5. Patient who has received a loading dose of clopidogrel, prasugrel or ticagrelor (commercial pack) for the index event or who are on chronic treatment of prasugrel, clopidogrel or ticagrelor (commercial pack)
6. Concomitant medication that may increase the risk of bleeding [e.g non steroidal anti-inflammatory drugs (NSAIDs), oral anticoagulant and / or fibrinolytics, planned or administered 24 hours before randomization]
7. Planned surgery during the study period
8. Any of the following conditions in the absence of a functioning implanted pacemaker: known SSS, second or third degree AVB, or documented syncope of suspected bradycardic origin.
9. Patient requiring dialysis
10. Known clinically important thrombocytopenia
11. Known clinically important anemia

12. Known pregnancy or lactation
13. Condition which may either put the patient at risk or influence the result of the study (e.g., cardiogenic shock or severe hemodynamic instability, active cancer, risk for non-compliance, risk for being lost to follow up)
14. Active involvement in the planning and/or conduct of the study (applies to both AstraZeneca staff and/or staff at the study site)
15. Previous randomisation in the present study
16. Participation in another clinical study with an investigational product or device study during the last 30 days or during the study.

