#### **5.6.8.2 CYP3A substrates or inducers**

Concomitant therapy with simvastatin or lovastatin at doses higher than 40 mg daily is not recommended. There are no restrictions to other statin therapies (ie, doses of simvastatin or lovastatin  $\leq$ 40 mg daily or any dose of any other statin is permitted). Standard monitoring of patients for possible statin associated myopathy should be done.

Co-administration of ticagrelor with CYP3A substrates with a narrow therapeutic index (eg, cyclosporine and quinidine) is not recommended.

Co-administration of ticagrelor with strong inducers of CYP3A is discouraged (eg, rifampin/rifampicin, rifabutin, phenytoin, carbamazepine, phenobarbital).

If treatment with such therapies is necessary, study medication dosing should be interrupted and then resumed if possible when administration of the inducer or narrow therapeutic index drug is no longer required.

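### Sections 5.6.7 and 5.6.8.2 of the protocol give incompatible instructions on ticagrelor for a patient who must take quinidine or cyclosporin

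*Protocol*

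**What the plan says.** Protocol section 5.6.7 concerns "potent P-glycoprotein (P-gp) inhibitors (e.g. verapamil, quinidine, cyclosporin" as drugs that may increase ticagrelor exposure, and notes that no data exist on the combination. For the patient who needs one of them it says: "If the association cannot be avoided, their concomitant use should be made with caution". It does not mention interrupting study medication, and it points to the Summary of Product Characteristics for further detail.

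Protocol section 5.6.8.2 says: "Co-administration of ticagrelor with CYP3A substrates with a narrow therapeutic index (eg, cyclosporine and quinidine) is not recommended". After a sentence on strong CYP3A inducers, it adds: "If treatment with such therapies is necessary, study medication dosing should be interrupted and then resumed if possible", the condition for resuming being "when administration of the inducer or narrow therapeutic index drug is no longer required".

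**The concern.** Quinidine and cyclosporin (spelled cyclosporine in 5.6.8.2) are examples in both sections. A patient taking either drug falls under both at once, and the site must either give the next ticagrelor dose or withhold it.

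Each choice carries a risk that the protocol itself describes. Continuing means giving ticagrelor with a drug that may raise its exposure, in a trial where bleeding is the main safety outcome. Interrupting means losing platelet inhibition in patients enrolled for primary PCI, many of them with a new stent.

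With about 120 centres in 10 to 15 countries, different sites can be expected to rely on different sections. Like patients would then differ in exposure, recorded interruptions and compliance status for no reason beyond which paragraph was read.

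**Working it through.** No figure in the plan is in dispute, so the check is mainly a comparison of texts.

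| | Section 5.6.7 | Section 5.6.8.2 |
|---|---|---|
| Drugs named | verapamil, quinidine, cyclosporin | cyclosporine, quinidine (plus a separate list of inducers) |
| Reason | P-glycoprotein inhibition, possible rise in ticagrelor exposure | narrow-therapeutic-index CYP3A substrate |
| Trigger | the combination cannot be avoided | the other drug is necessary |
| Action | use together, with caution | interrupt study medication, resume later if possible |

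**Step 1: overlap.** Quinidine and cyclosporin are in both lists. Verapamil is only in 5.6.7, so the conflict is limited to two named drugs.

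**Step 2: reach of the interruption rule.** It could be asked whether the rule in 5.6.8.2 covers only the inducers in the sentence before it. It does not: dosing resumes "when administration of the inducer or narrow therapeutic index drug is no longer required", and the two drugs are the section's own examples of narrow-index drugs.

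**Step 3: possible resolution elsewhere.**

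- Section 4.2, exclusion criterion 3, covers "Concomitant oral or intravenous therapy with strong cytochrome P450 3A (CYP3A) inhibitors which cannot be stopped for the course of the study". Its list names neither drug, and no other criterion names them. Either drug could also be started after randomisation.
- Sections 5.8.1 and 5.8.2, on temporary and permanent discontinuation, do not mention interacting drugs.
- The administrative changes appended to the protocol revise the synopsis and sections 5.4.2, 5.8.2, 6.4.5 and 6.4.7.1. None touches 5.6.7 or 5.6.8.2.
- Neither section refers to the other or states an order of precedence.

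**Step 4: size for one patient, from the protocol's own figures.**

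- Maintenance is 90 mg twice daily for 30 days: 30 × 2 = 60 doses. One reading gives all of them; the other gives none while the interacting drug is needed.
- Section 5.6.9 says the platelet effect has largely gone by 48 to 72 hours after stopping. At 12-hourly dosing that is 48/12 = 4 to 72/12 = 6 missed doses.
- Section 5.5.2 defines a recordable interruption as at least 4 missed doses, which is 4 × 12 = 48 hours. By the time an interruption reaches the recording threshold, the platelet effect is already at the start of that range.
- Section 5.7.1 calls a patient compliant if study medication was taken for more than 80% of the active period: 0.80 × 30 = 24 days. An interruption of 6 days or more therefore makes the patient non-compliant (30 − 6 = 24, which is not more than 24), while a patient kept on ticagrelor at another site would count as compliant.

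**The case against.** The strongest reply is that the two texts can be read in sequence. Section 5.6.7 is conditional on the combination being unavoidable; section 5.6.8.2 is conditional on the other drug being necessary. Interrupting ticagrelor is itself a way of avoiding the combination, so a site that follows 5.6.8.2 never reaches the fallback in 5.6.7. Advice to use caution does not oblige anyone to continue, so the interrupting site breaches neither section.

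This reading is possible, but the protocol does not state it. It needs an order of precedence that appears nowhere, and it leaves the permission in 5.6.7 without effect for two of the three drugs named there. A site that starts from 5.6.7 has no signal to look further.

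Several narrower points do stand:

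- Both sections use the word should. The interruption is a direct instruction but not an absolute requirement.
- The protocol gives no rate of use for either drug, so the number of patients and the length of any interruption are unknown.
- After the loading doses both arms receive the same ticagrelor regimen, so inconsistent handling of maintenance is not tied to the randomised comparison. The co-primary endpoints are read from the pre-PCI ECG and the initial angiogram, before maintenance begins. Only a patient already taking one of the drugs at Visit 1 could be affected at the loading-dose stage.
- Section 12.2.3 treats bleeding tests as non-confirmatory.
- Concomitant medication, and interruptions of at least 4 doses, are recorded under common rules, so most affected patients could be identified afterwards.
- The Summary of Product Characteristics may give a single instruction. It is not at hand, and it would not correct the protocol text.

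**Conclusion.** The contradiction is real. For quinidine and cyclosporin, one section permits ticagrelor to continue with caution where the other says it should be interrupted, on what is in practice the same trigger, and no text in the protocol decides between them.

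Its effect on the trial's statistics is slight: none on the sample size, and on the co-primary results at most through the rare patient already on one of these drugs at Visit 1. Its importance is for the individual patient, where the handling differs completely, and for the consistency of exposure, interruption and compliance data across sites.

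This assumes that at least some patients take either drug during the 30 days, which the eligibility criteria do not prevent. It should be corrected, although it does not threaten the main analysis.

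**What to change.** Reconcile sections 5.6.7 and 5.6.8.2 so that each drug named in both carries one instruction, stated once, with a cross-reference from the other section. If both texts are meant to remain, state which prevails for a drug that falls under both. The new wording should also say whether it applies to the blinded loading doses as well as to maintenance, since section 5.5.2 treats a missed blinded dose as a major deviation.

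Which instruction applies is for the sponsor's clinical pharmacology and safety staff; this review takes no position on it.

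The cost is an administrative change of about one paragraph, the route the sponsor has already used to clarify instructions to sites. Sample size, visit schedule and assessments are unaffected.

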### **5.6.8 CYP3A interactions**

#### **5.6.8.1 CYP3A inhibitors**

Strong inhibitors of this enzyme (eg, ketoconazole, itraconazole, voriconazole, telithromycin, clarithromycin [but not erythromycin or azithromycin], nefazadone, ritonavir, saquinavir, nelfinavir, indinavir, atazanavir, or over 1 litre daily of grapefruit juice) should not be coadministered with ticagrelor as plasma levels of ticagrelor would be substantially increased. If treatment with such therapies is necessary, study medication dosing should be interrupted and then resumed if possible when administration of the CYP3A inhibitor is no longer required.

#### **5.6.8.2 CYP3A substrates or inducers**

Concomitant therapy with simvastatin or lovastatin at doses higher than 40 mg daily is not recommended. There are no restrictions to other statin therapies (ie, doses of simvastatin or lovastatin  $\leq$ 40 mg daily or any dose of any other statin is permitted). Standard monitoring of patients for possible statin associated myopathy should be done.

Co-administration of ticagrelor with CYP3A substrates with a narrow therapeutic index (eg, cyclosporine and quinidine) is not recommended.

Co-administration of ticagrelor with strong inducers of CYP3A is discouraged (eg, rifampin/rifampicin, rifabutin, phenytoin, carbamazepine, phenobarbital).

If treatment with such therapies is necessary, study medication dosing should be interrupted and then resumed if possible when administration of the inducer or narrow therapeutic index drug is no longer required.

### **5.6.9 Surgery and other invasive non-cardiovascular procedures**

For urgent major surgery, if a 7 day window off treatment is not feasible, it should be noted that the average half-life of ticagrelor is about 12 hours. The effect on platelet function caused by ticagrelor will have largely dissipated in most individuals by 48 to 72 hours after discontinuation.

It should be noted that all patients in this study are also treated with ASA, an irreversible inhibitor of platelets, and this therapy should be handled according to physician discretion in case of surgery.

### **5.6.10 Other medications**

Other medication, which is considered necessary for the patient's safety and well-being, may be given at the discretion of the investigator(s) and recorded in the appropriate section of the eCRF.

## **5.7 Treatment compliance**

The administration of all medication (including investigational products) should be recorded in the appropriate sections of the Case Report Form.

### **5.7.1 Accountability**

The study medication provided for this study will be used only as directed in the protocol.

The study personnel will account for all study medication dispensed to and returned from the patient. This record keeping consists of a dispensing record including the identification of the person to whom the drug is dispensed, the quantity, and the date of dispensing.

Patients will be asked to return all unused study medication/ empty bottle to the investigational centre at visit 5 or at discontinuation visit. The Investigator will make an assessment in the eCRF regarding patient treatment compliance. If the patient has taken study medication for more than 80% of the active treatment period, the patient will be regarded as compliant.

Any study medication deliberately or accidentally destroyed must be recorded. Any discrepancy between dispensed and returned study medication should be explained.

The investigator or delegate will retain the returned medication until the trial monitor has checked the records for quantities of returned and unused tablets at a patient level. Following drug accountability, the trial monitor will advise on the appropriate method for destruction of unused study medication. It is preferable that all used and unused medication be destroyed at the site. Destruction of study medication must only be conducted by an authorized site. Signed certificate of destruction will be collected by the trial monitor.

